## 4.1. Study Population

All inclusion and exclusion criteria must be met for eligibility.

### 4.1.1. Inclusion Criteria

*A subject must meet all of the following criteria:*

1. Willing and able to complete the informed consent process.
2. 18 to 50 years of age.
3. Based on history and examination, must be in good general health and without history of any of the conditions listed in the exclusion criteria.
4. Willing to have blood samples collected, stored indefinitely, and used for research purposes.
5. Able to provide proof of identity to the satisfaction of the study clinician completing the enrollment process.
6. Screening laboratory criteria within 84 days prior to enrollment must meet the following criteria:
  - White blood cell count (WBC): 2,500-12,000/mm^3.
  - WBC differential: Within institutional normal range or accompanied by the Principal Investigator (PI) or designee approval.
  - Platelets: 125,000 – 400,000/mm^3.
  - Hemoglobin: Within institutional normal range or accompanied by PI or designee approval.
  - Creatinine:  $\leq 1.1 \times$  Upper Limit of Normal (ULN).
  - ALT:  $\leq 1.25 \times$  ULN.
  - AST:  $\leq 1.25 \times$  ULN.
  - Negative for HIV infection by an FDA approved method of detection.

#### *Female-Specific Criteria:*

7. If a woman is of reproductive potential and sexually active with a male partner, then she agrees to use an effective means of birth control from the time of study enrollment until the last study visit, or to be monogamous with a partner who has had a vasectomy.

8. Negative  $\beta$ -HCG (human chorionic gonadotropin) pregnancy test (urine or serum) on day of enrollment for women presumed to be of reproductive potential.

#### **4.1.2. Exclusion Criteria**

*A subject will be excluded if one or more of the following conditions apply:*

1. Prior receipt of licensed or investigational monoclonal antibody.
2. Weight  $> 115$  kg.
3. Any history of a severe allergic reaction with generalized urticaria, angioedema or anaphylaxis within the 2 years prior to enrollment that has a reasonable risk of recurrence during the study.
4. Hypertension that is not well controlled.
5. Woman who is breast-feeding, or planning to become pregnant during the study participation.
6. Receipt of any investigational study agent within 28 days prior to enrollment.
7. Any other chronic or clinically significant medical condition that in the opinion of investigator would jeopardize the safety or rights of the subject including (but not limited to): diabetes mellitus type I, chronic hepatitis; OR clinically significant forms of drug or alcohol abuse, asthma, autoimmune disease, infectious disease, psychiatric disorders, heart disease, or cancer.
8. Known hypersensitivity to hyaluronidase or any of the excipients in EDP.

### **4.2. Inclusion of Vulnerable Subjects**

#### **4.2.1. Participation of Children**

Children are not eligible to participate in this clinical trial because the study agent has not been previously evaluated in adults. If the product is assessed as safe for further study other protocols specifically designed for children may be conducted.

#### **4.2.2. Participation of NIH Employees**

NIH employees and members of their immediate families may participate in this protocol. We will follow the Guidelines for the Inclusion of Employees in NIH Research Studies and will give each employee a copy of the “NIH FAQs for NIH Staff Who are Considering Participation in NIH Research” published by Office of Human Research Subjects Protections on Research Involving NIH Staff as Subjects, Policy 404.

For NIH employee subjects, consent will be obtained by an individual who is independent of the employee’s team. If an NIH staff member seeks to enroll in research taking place within their own work unit or conducted by any of their supervisors, the employee will be:

- Informed that neither participation nor refusal to participate as a research subject will have an effect, either beneficial or adverse, on the subject’s employment, training or position at the NIH,
- When possible, consent should be obtained by an individual in a non-supervisory relationship with the subject, and

- When consent is conducted, a third party (e.g. a consent monitor) will be included through the Bioethics Consultation Service or another party independent of the research team or, if a consent monitor is not available, the consent process will be observed by another qualified investigator on the study who is independent of the NIH staff member's work unit and not a supervisor to the NIH staff member. If no such person exists, consent observation may be performed by any qualified investigator on the study. Protocol study staff will be trained on obtaining potentially sensitive and private information from co-workers or subordinates.

#### **4.2.3. Adult Subjects who Lack the Capacity to Consent**

Adults who are unable to provide initial informed consent are not eligible to enroll. Also, adults who permanently lose the capacity to provide on-going consent after initial consent and during the study will be discontinued from protocol participation as it is described in [Section 4.5](#)

### **4.3. Clinical Procedures and Laboratory Assays**

Evaluation of study product safety for this study will include laboratory studies, medical history, and physical assessment by clinicians, and subject self-assessment on a diary card for 3 days after product administration. The study schedule is provided in the Schedule of Evaluations, Appendix I. Total blood volume drawn from each subject will comply with the NIH CC Guidelines, which is available on the NIH intranet at the following link: <http://cc-internal.cc.nih.gov/policies/PDF/M95-9.pdf>.

#### **4.3.1. Recruitment and Retention Strategies**

Study enrollments will be conducted at the NIH Clinical Center. Study subjects will be recruited through the VRC's screening protocol, VRC 500 (NCT 01375530). The on-site and off-site Institutional Review Board (IRB)-approved advertising will be implemented. Per a recruitment plan described in the VRC 500 protocol, efforts will be made to include women and minorities in proportions similar to that of the community from which they are recruited.

#### **4.3.2. Screening**

All screening procedures for this study are described and will be completed through the Vaccine Research Center's screening protocol, VRC 500 (NIH 11-I-0164) used for all VRC IND studies conducted at the NIH Clinical Center. The Recruitment Plan per NIH Policy 302 for all VRC studies can be found in the NIH IRB approved VRC 500 protocol. Subjects will be recruited through Institutional Review Board (IRB)-approved advertising. Screening evaluations performed to determine eligibility for study participation will include medical history review, physical exam, and the clinical laboratory tests as detailed in the Schedule of Evaluations, Appendix I). No screening procedures will be done under protocol VRC 609.

Additional assessments of health may be conducted at screening based on clinical judgment. Screening evaluations for specific eligibility criteria must be completed within the time interval specified prior to enrollment for the given parameter and may be repeated, as needed, to confirm eligibility.

Blood samples for research can be drawn at any time during the screening period and are not required to be repeated if outside the screening period. Informed consent documents will be

reviewed. Counseling related to potential risks of the study product, pregnancy prevention and HIV risk-reduction will be performed. An Assessment of Understanding (AoU) will be completed in association with enrollment into VRC 609. Screening records will be kept to document the reason why an individual was screened but not enrolled.

#### **4.3.3. Enrollment, Study Days and Visit Numbers**

In this study, enrollment is defined as the assignment of a study identification number and study group schedule in the clinical database. A clinician will discuss the target dates and timing of the study product administration(s) and sample collections before completing an enrollment to help ensure that the subject can comply with the projected schedule.

Day 0 is defined as the day of first N6LS administration. Day 0 may occur on the same day as enrollment or up to 6 weeks after enrollment. This period may be increased with PI approval. If Day 0 does not coincide with enrollment, then the enrollment day may be referred to by a negative number of days (i.e., Day -1 to Day -42). For calculating elapsed days following Day 0, each subsequent calendar date is labeled by the next sequential “Study Day” as shown in the Schedule of Evaluations (Appendix I). Since there may be more than one research sampling timepoint of interest per study day, each sample collection timepoint has its own “Visit Number.” For this reason, there may be more than one visit number recorded on the same calendar date.

Medical history and Day 0 evaluations prior to the first study product administration are the baseline for subsequent safety assessments.

#### **4.3.4. Administration of N6LS**

All study product administrations will be completed according to the assigned group. For women of childbearing potential, a negative pregnancy test must be obtained prior to product administration that day. Refer to the pharmacy manual for study product preparation and administration instructions.

Prior to each product administration, temperature, blood pressure, heart rate (pulse) and weight will be recorded and a targeted physical examination will be conducted. All subjects will be observed for 4 hours after the first product administration. Subjects in the multi-dose groups will be observed for at least 2 hours after the second and third product administrations.

#### **IV Administration**

If a subject is assigned to an IV administration group, the IV access will be placed in an arm vein in an aseptic manner. A different site may be used for collection of PK blood samples; however, the same site may be used after flushing the line if another site is not available. N6LS will be administered with approximately 100 mL of normal saline IV (as described in the IB) over about 15-30 minutes, with a target of 30 minutes for the initial infusion for each subject. Infusions lasting longer than 30 minutes are allowed. If the subject experiences side effects during the infusion, the rate of infusion may be slowed or stopped to alleviate the symptoms.

#### **SC Administration without rHuPH20**

If a subject is assigned to a SC administration group, the SC administration site(s) to be used must be assessed as acceptable by the clinician and the subject. The preferred SC administration

site is the abdomen, but the upper arm or thigh may be used. Given the weight criterion in this study, the maximum volume needed to administer a 5 mg/kg SC dose is not expected to exceed 5.75 mL. The SC dose will be administered by standard needle in a maximum volume of about 2.5 mL per injection site. Up to 4 SC injection sites may be used if deemed necessary by the clinician. SC administration sites should be at least 2 inches apart.

### **SC Administration with rHuPH20**

If a subject is assigned to a SC administration group, the SC administration site(s) to be used must be assessed as acceptable by the clinician and the subject. The preferred SC administration site is the abdomen. N6LS will be mixed with **rHuPH20** in the pharmacy and then administered via standard Medfusion 3500 syringe pump (or equivalent) in one infusion site at a rate of no more than 3 mL/minute. Given the weight criterion in this study, the maximum volume needed to administer a 20 mg/kg SC dose is not expected to exceed 23.42 mL. If the subject experiences side effects during the infusion, the rate of infusion may be slowed or stopped to alleviate the symptoms. Procedures for all N6LS preparations and administrations are described in Section 7.

#### **4.3.5.     Solicited Adverse Events and Clinical Follow-up**

Subjects will be given a 3-day diary (paper or electronic-based), a thermometer, and a measuring tool. The subjects will use the diary daily as a memory aid to record their highest temperature, local and systemic symptoms, and concomitant medications taken for 3 days after any product administration. Subjects will be provided training on diary completion, proper thermometer usage, and the use of the measuring tool to measure injection site bruising, swelling and redness. Completion of diary card training will be noted in the source documents. Note that while the electronic diary is preferred, subjects will have the option to use a paper diary instead. The paper diary if used, will be transcribed into the study database and stored in the subject file for monitoring purposes.

The signs and symptoms solicited by diary will include systemic events of unusually tired/feeling unwell, muscles aches (outside the injection site), headache, chills, nausea and joint pain; and local (at the product administration site) events of pain/tenderness, swelling, redness, bruising, and pruritus. Subjects will record their highest measured temperature daily for assessment of fever and largest measured diameter of redness, swelling, and bruising at the injection site. Subject diaries will be reviewed by a clinician for accuracy and completeness at follow-up visits. No attribution assessment will be performed for solicited events reported in the diary. Clinicians will follow and collect resolution information for any reactogenicity symptoms that are not resolved within 3 days.

Diary card data will be available in real-time for subjects who use the electronic diary. The clinician may contact the subject by phone if any moderate or severe side effect is reported. Events that may require a clinic visit include rash, urticaria, fever of 38.6°C (Grade 2) or higher lasting greater than 24 hours or significant impairment in the activities of daily living (ADL) (such as those consistent with Grade 2 or higher impairment). Additionally, arthralgia or other clinical concerns may prompt a study visit based on the judgment of a study clinician.

Clinical laboratory assays and clinical evaluations will assess safety and tolerability at specified intervals after each administration. Throughout the study, clinicians will also assess subjects for

any changes in symptoms. Any new or concerning symptoms will be fully assessed to include specialty consultation at the NIH Clinical Center as indicated clinically.

#### **4.3.6. Pharmacokinetics**

PK samples will be collected as close as reasonably possible to the target timepoints. However, actual time of collection is critical for PK analysis and will be recorded for all samples. The PK timepoints are shown in the Schedule of Evaluations (Appendix I).

#### **4.3.7. Schedule of Evaluations**

The Schedule of Evaluations (Appendix I) provides details on the study schedule and the permitted visit windows. Schedule 1 is for the IV dose escalation groups receiving one infusion (Groups 1, 3, and 4). Schedule 2 is for the SC dose group receiving one injection (Group 2). Schedule 3 and Schedule 4 are for the groups receiving repeat dosing: Group 5 (5 mg/kg SC) and Group 6 (20 mg/kg IV), respectively. Schedule 6 is for the N6LS+ rHuPH20 SC dose groups receiving one infusion at N6LS dose levels of 5 mg/kg (Group 7) or 20 mg/kg (Group 8). After enrollment, deviations from the visit windows are discouraged but will be permitted at the discretion of the PI or designee; and will be recorded as protocol deviations.

If product administration is discontinued for a Group 5 or 6 subject assigned to receive repeat product administrations, then the study schedule may be modified and the subject will be followed for 24 weeks after the last product administration received. Schedule 5 of the SOE outlines this altered schedule. Briefly, subjects will be followed according to the assigned group visit schedule until the 12th week after their last product administration where they will complete the protocol according to Schedule 5 starting at Visit 11 for those who received only one product administration or Visit 17 for those who received two product administrations.

Additional visits and blood draws may be scheduled during the study if needed to assess subject safety or for sample collection for immunological testing. After study completion, subjects may be invited to participate in one of the VRC sample collection protocols (VRC 200 or VRC 900) for follow-up sample collection.

Any evaluation for an AE or possible exacerbation of a pre-existing condition may be evaluated at study team discretion as a “protocol related” evaluation.

#### **4.3.8. Concomitant Medications**

Only routine prescription medications will be entered in the database at the time of enrollment. Subsequently, concomitant medications associated with an adverse event (AE) that requires expedited reporting or the development of a new chronic condition requiring ongoing medical management will be recorded in the database. Receipt of a FDA-approved vaccine at any time during the study will be recorded in the database (clinicians should work with subjects regarding the timing of licensed vaccines relative to study product administration). Otherwise, concomitant medications taken throughout the study will be recorded in the subject’s chart as needed for general medical documentation but will not be recorded in the database.

#### 4.4. Criteria for Dose-Escalation and Repeat-Dosing

Dose groups will be enrolled sequentially in a staged manner, depending on the outcome of planned PSRT Data Reviews. These reviews will determine if dose-escalation to the next higher N6LS dose level may occur, and if 2nd and 3rd doses (repeat-dosing) may be administered to applicable dose groups (Table 2). Whenever possible and as data are available, PSRT Data Reviews for dose-escalation and repeat-dosing will be held concurrently as follows:

**Table 2: Schema for Dose-escalation and Repeat-Dosing PSRT Data Reviews**

Data Review Objective	Minimum Evaluable Safety Data*	Favorable Review Outcome
Review #1		

 
Dose-escalation from 5 to 20 mg/kg IV
 
Repeat-dosing at 5 mg/kg SC
 
	
 
All post-administration safety data from Day 0 through at least the “Day 14” visit in at least 3 subjects in Group 1.
 
All post-administration safety data from Day 0 through at least the “Day 14” visit in at least 3 subjects in Group 2 or 5.
 
	
 
Proceed with enrollments into Groups 3 and 6.
 
Proceed with second and third doses in Group 5.
 

Review #2		

 
Dose-escalation from 20 to 40 mg/kg IV
 
Repeat-dosing at 20 mg/kg IV
 
	
 
All post-administration safety data from Day 0 through at least the “Day 14” visit in at least 3 subjects in Group 3 or 6.
 
	
 
Proceed with enrollments into Group 4.
 
Proceed with second and third doses in Group 6
 

Review #3		

 
Dose-escalation from 5 to 20 mg/kg N6LS with rHuPH20 by SC infusion
 
	
 
All post-administration safety data from Day 0 through at least the “Day 14” visit in at least 3 subjects in Group 7
 
	
 
Proceed with enrollments into Group 8.
 

If the first product administration is not completed or there are discontinuations from the study before there are sufficient data to conduct the dose escalation review, then extra subjects may be enrolled in order to have the requisite data on at least 3 subjects at the dose level and route being evaluated. Additionally, AEs assessed as related to the study product at the time of a dose-escalation review may be judged by the PSRT to warrant adding additional subjects at a given dose group.

The IRB will be provided with documentation of the safety review process and notification of the dose-escalation. Consultation with the IRB and notification of the FDA, if needed, as per study pause criteria (Section 4.6) will occur if indicated by the review. One outcome of a dose-escalation review may be to recommend evaluation of additional subjects at the current dose and reassess for safety before proceeding to a higher dose.

#### **4.5. Criteria for Subject Discontinuation from Protocol Participation**

A subject may be discontinued from protocol participation for the following reasons:

- Subject voluntarily withdraws;
- The IND Sponsor or regulatory authorities stop the study;
- The PI assesses that it is not in the best interest of the subject to continue participation in the study; or
- Severe non-compliance as determined by the PI.

#### **4.6. Criteria for Discontinuation of N6LS or N6LS+ rHuPH20 Administration**

Under certain circumstances, a subject may be prohibited from receiving further study product administrations. These include:

- Pregnancy (female subjects only);
- Grade 3 adverse event assessed as related to N6LS or N6LS+rHUPH20 (with the exception that self-limited Grade 3 solicited reactogenicity will not require discontinuation of product administration);
- Grade 4 adverse event assessed as related to N6LS or N6LS+rHUPH20;
- Immediate hypersensitivity reaction associated with N6LS or N6LS+rHUPH20;
- Intercurrent illness that is not expected to resolve prior to the next scheduled study product administration AND for which PI (or designee) believes is in the best interest of the subject to restrict further exposure;
- Repeated failure to comply with protocol requirements;
- Co-enrollment into a study to receive another investigational research product prior to completion of the requisite study follow-up following the last N6LS product administration;
- The IND sponsor or the study PI decide to terminate the study;
- The IRB, Office for Human Research Protections (OHRP) or the FDA halt the study.

Subjects who have received at least one dose of N6LS but have been discontinued from further study product administrations, will continue with follow-up as shown in the Schedule 5 of the SOE with the exception that research sample collections will be discontinued for pregnant women or others in which it is contraindicated.

#### **4.7. Criteria for Pausing and Resuming the Study**

Administration of either study product (N6LS or N6LS+ rHuPH20) and new enrollments will be paused by the PI if any of the following criteria is met:

- **One** (or more) subject experiences a serious adverse event (**SAE**) that is assessed as related (possible, probably, or definitely) to the study product, or

- **Two** (or more) subjects experience the same **Grade 3 or higher AE** that is assessed as related (possible, probably, or definitely) to study agent (other than self-limited Grade 3 AEs that resolve during the solicited reactogenicity period).

In the event of a pause, the IND Sponsor Medical Officer (MO) and the PSRT will be promptly notified.

Plan for Review of Pauses and Resuming Rules:

Study product administration and enrollments would resume only if review of the AEs that caused the pause results in a recommendation to permit further study product administrations and study enrollments. The reviews to make this decision will occur as follows:

- **Pauses for related SAEs:** The IND Sponsor Medical Officer (MO), with participation by the PI, will conduct the review and make the decision to resume, amend or close the study. The IRB and FDA will be notified accordingly.
- **Pauses for Grade 3 or higher related AEs:** The IND Sponsor MO, in consultation with the PI, will conduct the review and make the decision to resume, amend or close the study for the Grade 3 or higher AEs that meet criteria for pausing the study. As part of the pause review, the reviewers will also advise on whether the study needs to be paused again for any subsequent events of the same type. The FDA and the IRB will be notified of Grade 3 or higher pause reviews and of the IND Sponsor's decisions.

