## **5. SAFETY AND ADVERSE EVENTS**

### **5.1. Adverse Events**

An adverse event (AE) is any untoward or unfavorable medical occurrence in a human subject, including any abnormal sign (e.g., abnormal physical exam or laboratory finding), symptom, or disease temporally associated with the use of study treatment, whether or not considered related to the study treatment.

Severity of AEs will be assessed using the *DAIDS Table for Grading the Severity of Adult and Pediatric Adverse Events*, Corrected Version 2.1 [July 2017]. Available from: [https://rsc.techres.com/docs/default-source/safety/division-of-aids-\(daids\)-table-for-grading-the-severity-of-adult-and-pediatric-adverse-events-corrected-v-2-1.pdf](https://rsc.techres.com/docs/default-source/safety/division-of-aids-(daids)-table-for-grading-the-severity-of-adult-and-pediatric-adverse-events-corrected-v-2-1.pdf). Additional information can be found in Appendix II. This grading scale has been used in all prior studies with other HIV-1 bNAbs and will allow for a direct comparison of safety across all available HIV-1 bNAbs.

Reporting of all AEs will occur during the period from first study product administration through 56 days after each study product administration. After this through completion of study participation only serious adverse events (SAEs) and new chronic medical conditions that require ongoing medical management will be recorded as AEs in the study database.

When a subject who receives N6LS coadministered with rHuPH20 experiences an AE assessed by the investigator as related to study product, this attribution reflects relatedness to N6LS and not rHuPH20. Any differences in safety and tolerability between the 5 mg/kg SC N6LS dose without rHuPH20 and 20 mg/kg N6LS SC dose with rHuPH20 will be interpreted as a dose-response difference of N6LS delivered subcutaneously. The extant experience with rHuPH20 indicates that rHuPH20 itself does not confer a unique set of AEs and this protocol will not specifically evaluate rHuPH20 itself for safety and tolerability.

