### **8.2. Risk/Benefit Assessment**

#### **8.2.1. Potential Risks**

##### Risks of N6LS and mAb Administration

Typically, the side effects of MAbs are mild but may include reactions at injection site (pain, redness, bruising, swelling), fever, chills, rigors, nausea, vomiting, pain, headache, dizziness, shortness of breath, bronchospasm, hypotension, hypertension, pruritus, rash, urticaria, angioedema, diarrhea, tachycardia or chest pain. Up to Grade 3 injection site erythema has been observed after N6LS+ rHuPH20 injection, and some injection site reactions have lasted up to six weeks before completely resolving. Clinical use of MAbs that are targeted to cytokines or antigens associated with human cells may be associated with an increased risk of infections [33]; however, this is not expected to be a risk for a MAb targeted to a viral antigen.

Administration of MAbs may cause immune reactions such as acute anaphylaxis, serum sickness and the generation of antibodies. However, these reactions are rare and more often associated with MAb targeted to human proteins or with the use of murine monoclonal antibodies which would have a risk of human anti-mouse antibodies [33]. In this regard, as N6LS is expected to have a low risk of such side effects since it is directed against a viral antigen and is human in origin.

Published experience with other human MAb directed against the cell surface targets on lymphocytes have shown that infusion of a MAb may be associated with cytokine release, causing a reaction known as "cytokine release syndrome" (CRS) [34]. Most infusion-related events occur within the first 24 hours after beginning administration. Severe reactions, such as anaphylaxis, angioedema, bronchospasm, hypotension and hypoxia, are infrequent and more often associated with MAbs targeted to human proteins or when a non-human MAb, such as a murine MAb, is used [33]. Specifically, with regard to the rare CRS reactions, these generally

occur within the first few hours of beginning the infusion and are more common with the first MAb infusion received. This is because the cytokine release is associated with lysis of the cells targeted by the MAb and the burden of target cells is greatest at the time of the first MAb treatment. With licensed therapeutic MAbs, CRS is managed by temporarily stopping the infusion, administration of histamine blockers and restarting the infusion at a slower rate [35].

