**Assessment of Causality Relationship of an Adverse Event to Study Product:**

The relationship between an adverse event (AE) and the product will be assessed by the investigator on the basis of his or her clinical judgment and the definitions below.

- **Definitely Related.** The AE and administration of study product are related in time, and a direct association can be demonstrated.
- **Probably Related.** The AE and administration of study product are reasonably related in time, and the AE is more likely explained by study product than other causes.
- **Possibly Related.** The AE and administration of study product are reasonably related in time, but the AE can be explained equally well by causes other than study product.
- **Not Related.** There is not a reasonable possibility that the AE is related to the study product.

For purposes of preparing data reports in which AE attributions are limited to “**Related**” or “**Not Related**”, in this protocol, the “Definitely, Probably and Possibly” attributions will be mapped to the “**Related**” category. The definitions that apply when these two categories alone are used are as follows:

- **Related** – There is a reasonable possibility that the AE may be related to the study product.
- **Not Related** – There is not a reasonable possibility that the AE is related to the study product.

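### The pause rule in 4.7 needs an attribution that 4.3.5 withholds from diary-solicited events, so read literally a lasting Grade 3 or any Grade 4 non-serious solicited reaction cannot trigger it

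*Combined protocol and SAP*

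**What the plan says.** Section 4.7 has two mandatory pause criteria. The first is a single related SAE. The second is met when two or more "subjects experience the same Grade 3 or higher AE that is assessed as related (possible, probably, or definitely) to study agent", with one exemption: "other than self-limited Grade 3 AEs that resolve during the solicited reactogenicity period".

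Section 4.6, on stopping further doses in an individual, lists a related Grade 3 event and qualifies it: "self-limited Grade 3 solicited reactogenicity will not require discontinuation of product administration". A related Grade 4 event is listed without qualification.

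Section 4.3.5 defines a 3-day diary of local and systemic symptoms. It then states: "No attribution assessment will be performed for solicited events reported in the diary". For symptoms that continue, it adds: "Clinicians will follow and collect resolution information for any reactogenicity symptoms that are not resolved within 3 days".

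Two general rules bear on the point. Section 5.1 says "Reporting of all AEs will occur during the period from first study product administration through 56 days after each study product administration". Appendix II says that the relationship of an AE to product "will be assessed by the investigator on the basis of his or her clinical judgment and the definitions below". Neither mentions solicited events.

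**The concern.** The second criterion works only on events with a recorded relationship to product, and 4.3.5 tells staff not to record one for the events that the diary solicits. A solicited reaction that stays at Grade 3 past the diary period lies outside the exemption, yet never acquires the status that the criterion requires. The same is true of a Grade 4 solicited event of any duration, because the exemption names Grade 3 only.

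This matters most for Groups 7 and 8. Each subject there gets one dose, so 4.6 has no later dose to withhold, and the second bullet of 4.7 is the only mandatory pause for non-serious toxicity. Local reactions are also the most foreseeable severe event. Section 8.2.1 reports: "Up to Grade 3 injection site erythema has been observed after N6LS+ rHuPH20 injection". Section 1.4.1 reports redness ranging up to severe among 6 of 12 SC recipients, and Section 4.3.4 allows up to 23.42 mL at one site for the 20 mg/kg dose.

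**Working it through.** The plan states no operating characteristic for the pause rule, so there is no figure to reproduce. The check is mainly textual.

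**Texts side by side**

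1. *What 4.7 leaves in.* The exemption removes Grade 3 events that are self-limited and resolve in the solicited period. A Grade 3 reaction that outlasts the period, and any Grade 4 reaction, stay in.
2. *What 4.7 needs.* The event must have been assessed as related.
3. *What 4.3.5 supplies.* No attribution for diary-solicited events; for persistent ones, follow-up and resolution data only.
4. *What 4.6 presupposes.* It carves solicited reactogenicity out of related Grade 3 events. That carve-out has a purpose only if solicited events can be assessed as related.
5. *Whether a general rule overrides 4.3.5.* Section 5.1 and Appendix II cover AEs at large. Neither says that a persistent diary event is re-entered and attributed.
6. *What the analysis expects.* Section 6.3.3 tabulates solicited events by severity and group, and only unsolicited AEs by severity and relationship. That matches the no-attribution rule.

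Steps 1 and 4 point to counting these events. Steps 2 and 3 together prevent it, and steps 5 and 6 do not resolve the conflict.

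**Illustration of size**

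Subjects left to dose, from Section 1.4.1 (cut of 4 August 2021) and Table 1: 26 dosed in all, 22 of them in Groups 1-6, so 26 − 22 = 4 in Groups 7-8. Check by route: Groups 1-6 had 22 − 14 IV = 8 SC, and 12 SC − 8 = 4. Planned 5 + 5 = 10, leaving 10 − 4 = 6.

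Let p be the chance per subject of a Grade 3 site reaction lasting past the diary period. The text available for this review gives no value, so p is assumed. If every such event is attributed and judged related:

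- none on record: P(X ≥ 2) = 1 − (1−p)^n − n·p·(1−p)^(n−1)
- one on record: P(X ≥ 1) = 1 − (1−p)^n

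Example, n = 6 and p = 0.1: 1 − 0.5314 − 0.3543 = 0.114, and 1 − 0.5314 = 0.469.

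| Subjects left | On record | p = 0.05 | 0.1 | 0.2 | 0.3 |
|---|---|---|---|---|---|
| 6 | none | 0.033 | 0.114 | 0.345 | 0.580 |
| 6 | one | 0.265 | 0.469 | 0.738 | 0.882 |
| 3 | none | 0.007 | 0.028 | 0.104 | 0.216 |
| 3 | one | 0.143 | 0.271 | 0.488 | 0.657 |

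On the literal text every entry is 0 through this criterion. The rows for three subjects are shown because the protocol cites material later than the cut (December 2021 in Section 1.4.2, February 2022 in Section 2.2), so fewer than six may remain.

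For the rates assumed, these are upper limits. Section 4.7 needs the *same* AE in two subjects, whereas the calculation lets redness in one subject match swelling in another, and it takes every event as judged related. It also assumes independent subjects, one rate across Groups 7 and 8, no serious events and no replacements.

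**The case against.** The strongest reply is that the sections can be read together. The bar in 4.3.5 concerns events reported in a 3-day diary. A reaction still present afterwards is under clinician follow-up, fits the AE definition in 5.1, falls within the 56-day reporting window and so gets an Appendix II assessment. The exemption in 4.7 also names a time window and not solicited events, so it could be serving unsolicited Grade 3 events that resolve quickly. Section 4.6 does name solicited reactogenicity, but governs individual dosing.

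Much of this stands. Counting is the more plausible intent, and staff may well act on it. But no sentence says so, and the one sentence that addresses solicited events directly says the opposite.

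The second reply is that protection remains, and it does. The related-SAE pause applies to serious events. Section 8.9 provides daily Safety Officer review and weekly PSRT review, electronic diary data arrive in real time, and Table 2 requires safety data through Day 14 in at least three Group 7 subjects before Group 8 opens. The medical officer and the investigator who would handle a Grade 3 pause both sit on the PSRT. These reviews are discretionary in effect; what the literal reading removes is the automatic halt and the IRB and FDA notification that goes with it.

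A reader might go further and infer that severe, lasting reactions have already occurred in this trial and that a pause was missed. The documents do not support that. Section 8.2.1 reports Grade 3 erythema and, separately, some reactions lasting up to six weeks. The six-week moderate to severe erythema in Section 1.4.1 describes CD4-binding-site antibodies as a class. In the text available for this review, no N6LS reaction is described as both Grade 3 and persistent.

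**Conclusion.** Sections 4.7 and 4.3.5 conflict, and the conflict should be removed before further Group 7-8 dosing. On the literal text, a persistent Grade 3 or any Grade 4 non-serious solicited reaction cannot trigger the second pause criterion. That conclusion rests on wording alone and needs no assumed rate. It does not extend to saying that the pause rule as a whole fails, or that these groups lack safety oversight.

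The size is uncertain. The tabulated probabilities show only that the difference between the two readings could range from negligible to substantial. They should not be presented as the trial's operating characteristics. If two or more subjects already have the same qualifying event on record, the criterion would be met as soon as those events are attributed as related.

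**What to change.** In Section 4.3.5, directly after the no-attribution sentence, add:

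*Exception: any Grade 3 solicited event not resolved by the end of the 3-day diary period, and any Grade 4 solicited event, will have its relationship to study product assessed under Appendix II; if assessed as related, it counts toward Sections 4.6 and 4.7. It remains tabulated as a solicited event.*

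The condition on a related result keeps the investigator's judgement in place and avoids counting events judged not related. Keeping the event in the solicited table leaves 6.3.3 unchanged. Attribute any qualifying events already on record before dosing more Group 7-8 subjects, so that the count is current. If the sponsor does not want these events to count, the exemption in 4.7 should say that instead.

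The cost is one amended sentence with IRB approval and attribution of whatever qualifying events are on record; no new visits, subjects or committee. The real downside is that a pause becomes possible, perhaps at once, for persistent Grade 3 site reactions of a kind that has resolved without sequelae in the class. Section 4.7 limits that cost, because the pause review already advises whether later events of the same type need another pause.
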